4.5.2 Replacement of Subjects

Approximately 20 healthy subjects are planned for enrollment and will be randomized to one of the six treatment sequences. Up to 4 subjects may be qualified as replacements and replacement subjects (if needed) must complete the treatment period. A replacement subject will receive the same treatment as the subject being replaced. Thus, a maximum of 24 subjects will be exposed to study drug and procedures during the study.

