3.1 Study Design

This study will be a randomized, unblinded, three-way crossover study to determine naloxone plasma concentration after administration of multiple doses of intranasal (IN) naloxone.

Table 3-1: Study Schedule

Day -1	Day 1	Days 2-3	Day 4	Days 5-6	Day 7	Day 8
Check-in	Treatment Period 1	Washout	Treatment Period 2	Washout	Treatment Period 3	Check-out

The following 3 treatments will be evaluated in a randomized order over the 3 treatment periods.

Table 3-2: Study Treatments

Treatment	Description
A	Four 4 mg IN naloxone doses (1 dose every 2.5 min; L at 0 min, R at 2.5 min, L at 5 min, R at 7.5 min)
B	Four 4 mg IN naloxone doses (2 doses every 2.5 min; L and R at 0* min, L and R at 2.5* min)
C	Two 4 mg IN naloxone doses (L at 0 min, R at 2.5 min)

*L = Left Nostril, R = Right Nostril, * doses will be ~5 seconds apart (one after the other)*

Healthy subjects will be randomized to one of six treatment sequences (i.e., ABC, ACB, BAC, BCA, CAB, CBA). FDA will prepare the randomization schedule. Subjects will report to the study site for screening from Days -28 to -2 and then will return to the site on Day -1 for baseline assessments and check-in. After check-in (Day -1), subjects will receive dosing for the 3 respective treatment periods on Days 1, 4 and 7. There will be two days of washout between each treatment period. Participants will be confined in the study clinic from Day -1 until the morning of Day 8. On dosing days, dosing will occur as per the treatment description and PK assessments will occur at the following time points:

- PK assessment: 0 (pre-dose), 2, 4.5, 7, 10, 12.5, 15, 20, 30, 45, 60, 120, 180, 240, 360, and 720 minutes

The subject should remain fully supine for approximately one-hour post-dose. Subjects should be instructed not to breathe through the nose during administration of the nasal spray into the nose. Subjects will be instructed to leave their masks off for twenty minutes after drug administration.

A summary of all assessments prior to and following study drug administration on Day 1, is described in the Protocol, Schedule of Events.

Subjects will be discharged from the study after completion of all study procedures. If a subject discontinues from the study prematurely, all procedures scheduled for the end of the study will be performed.

4. Study Endpoints

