Based on these considerations and the concentration ratios and CVs in Table 4-1, a sample size was determined so that at least one of the planned time points would have greater than 90% power at a 0.0221 significance level for a one sided, log-transformed paired comparison (for the primary endpoint). For concluding an increase in naloxone concentration for Treatment A compared to Treatment C at 15 minutes, at least 12 subjects would be necessary assuming a 1.78-fold increase in exposure and 48% CV for the treatments. For concluding an increase in naloxone concentration for Treatment B compared to Treatment C at 10 minutes, at least 12 subjects would have the desired power assuming a 2-fold increase in exposure and 68% CV for the treatments. The sample size was further increased to 20 subjects to account for discontinuations and situations where the CV values in Table 4-1 may be underestimated for repeat naloxone dosing.

5. Analysis Populations

The PK population will include all subjects who receive study drug and have at least one estimable PK parameter after dosing. The safety population will include all subjects who receive

at least 1 dose of the study drug. The analysis population will include all subjects in the PK population with sufficient data to calculate PK parameters. Only subjects with results from two or more periods will be included in comparisons. Treatment in all analysis populations will be assigned based upon the treatment which the subjects actually received.

6. Data Screening and Acceptance

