6.1 Handling of Missing and Incomplete Data

The following approaches will be used for the handling of missing and incomplete data:

- Missing PK data (e.g., skipped plasma sample collected) will not be imputed.
- Missed dose, dose administered outside the window, or other issues with dose administration (e.g., product delivery fails) will result in PK data from that period for that subject being excluded from all treatment arm comparisons and summary statistics from that time point forward. Other situations, such as a subject sneezing in close proximity to dosing will be carefully documented by study staff and handling of these cases will be determined and documented before any concentration data is available.
- PK samples collected outside the protocol-defined sampling window (i.e., more than \pm 0.5 minute from the scheduled time for the first 15 minutes of collections) will be excluded from analyses comparing naloxone concentrations at the specific time point that is outside the window.
- PK measurements below the lower limit of quantification will be set to zero for all analyses.

7. General Statistical Considerations

All data will be presented in data listings. Data from subjects excluded from an analysis population will be presented in the data listings, but not included in the calculation of summary statistics. Demographic and baseline characteristics will be summarized overall and by treatment for all subjects.

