7.3.2 Dose Proportionality

Dose proportionality based on C_{max} , AUC_{0-t} , and AUC_{0-inf} will be compared between each of the three naloxone treatments as secondary endpoints. The 4-dose naloxone arms (separate comparisons for 1 dose every 2.5 minutes and 2 doses every 2.5 minutes) will be compared with the 2-dose naloxone arm (1 dose every 2.5 minutes). An additional comparison will be performed between the 4-dose naloxone arm B (2 doses every 2.5 minutes) as test and 4-dose naloxone arm A (1 dose every 2.5 minutes) as reference.

Dose-adjusted values for C_{max} , AUC_{0-t} , and AUC_{0-inf} will be calculated based on noncompartmental PK parameter results, normalized to per mg of naloxone administered. Using linear mixed-effects modeling, comparisons of log-transformed dose-adjusted PK parameters will be performed. Treatment will be a fixed effect. Subject will be included as a random effect on the intercept. Treatment differences on the log-scale will be estimated for the PK parameters. Geometric mean ratio and 90% CIs will be obtained by exponentiation of the treatment effect and 90% CIs based on the log-transformed scale. Dose-proportionality will be concluded if the confidence interval includes 1.

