7.3.3 Plasma Pharmacokinetics

The following PK parameters will be determined for naloxone for each subject across all treatments:

- **AUC from time 0 to the sampling time corresponding to the last quantifiable concentration (C_{last}) (AUC_{0-t})**

AUC_{0-t} will be calculated according to the linear trapezoidal rule from time 0 minutes to the last quantifiable concentration.

- **AUC from time 0 extrapolated to infinity (AUC_{0-inf})**

AUC_{0-t} will be extrapolated to infinity from the AUC from time 0 to the sampling time corresponding to the last quantifiable concentration plus the last quantifiable concentration divided by K_{el} , as follows:

$$AUC_{0-inf} = AUC_{0-t} + C_{last}/K_{el}$$

- **Partial AUCs (pAUC) over time intervals of 0 to 7 (pAUC₀₋₇), 0-10 (pAUC₀₋₁₀), 0-12.5 (pAUC_{0-12.5}), 0-15 (pAUC₀₋₁₅), 0-20 (pAUC₀₋₂₀), and 0-30 (pAUC₀₋₃₀) minutes**
pAUC will be calculated according to the linear trapezoidal rule from time 0 minutes to 7, 10, 12.5, 15, 20, and 30 minutes after time from first dose
- **Maximum concentration (observed peak drug concentration) (C_{max})**
 C_{max} will be read directly from the observed concentrations.
- **Time at which C_{max} occurs (T_{max})**
 T_{max} will be read directly from the observed concentrations as the blood sampling time corresponding to C_{max} . The earlier time will be reported in cases where the same C_{max} value is observed for a subject at multiple time points
- **Terminal half-life ($t_{1/2}$)**
The terminal half-life will then be calculated using the elimination rate constant as:
$$t_{1/2} = \ln(2)/K_{el}$$
- **K_{el}**
The terminal elimination rate constant, which will be determined from the terminal slope of the log-concentration curve using linear regression

The PK parameters will be analyzed using noncompartmental methods based on actual sampling times. Plasma concentrations below the limits of quantification will be set to zero for the purpose of this analysis (see Section 6). AUC_{0-inf} , $t_{1/2}$, and K_{el} for naloxone by treatment and subject will only be included if the subject has 3 or more concentration values on the terminal portion of the pharmacokinetic curve and with an adjusted coefficient of determination (R^2) greater than 0.80.

These PK parameters will be summarized using descriptive statistics (number of subjects, mean, SD, CV, median, minimum, and maximum) for naloxone.

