9.1 Randomization schedule

This is a 3-period, unblinded, crossover study where approximately 20 subjects will be enrolled to receive either two or four administrations of 4 mg intranasal naloxone following different administration schedules. Healthy subjects will be randomized to one of six treatment sequences (i.e., ABC, ACB, BAC, BCA, CAB, CBA), where treatment codes are summarized in the table below. The first 18 subjects enrolled will be randomized in blocks of 6. The remaining two subjects will be randomly placed in 2 of the 6 treatment sequences. The study plans for 1:1 enrollment of males and females, but the randomization will not account for sex and treatment sequence interactions.

Table 9-1: Treatment Codes and Treatment Names

Treatment Code	Treatment Name
A	Four 4 mg IN naloxone doses (1 dose every 2.5 min; L at 0 min, R at 2.5 min, L at 5 min, R at 7.5 min)
B	Four 4 mg IN naloxone doses (2 doses every 2.5 min; L and R at 0* min, L and R at 2.5* min)
C	Two 4 mg IN naloxone doses (L at 0 min, R at 2.5 min)

10. References

NARCAN Nasal Spray Label, dated 08/06/2020. Obtained from
https://www.accessdata.fda.gov/drugsatfda_docs/label/2020/208411Orig1s004lbl.pdf

Pocock, S. (1977). Group Sequential Methods in the Design and Analysis of Clinical Trials. *Biometrika*, 64(2), 191-199.

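### The dose-proportionality model omits period in a three-period crossover, and any CI widening that results favours concluding proportionality

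*SAP*

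**What the plan says.** SAP 7.3.2 names the effects in the model: "Treatment will be a fixed effect. Subject will be included as a random effect on the intercept". The response is the log of dose-adjusted Cmax, AUC0-t or AUC0-inf, and the output is a geometric mean ratio with a 90% CI. The decision rule in the same section is: "Dose-proportionality will be concluded if the confidence interval includes 1". Protocol 4.9.5 adds no period or sequence term, and Protocol 4.9.1 (Analysis Populations) gives the SAP precedence where the two differ.

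The design is a crossover: "The following 3 treatments will be evaluated in a randomized order over the 3 treatment periods" (SAP 3.1), with six sequences. Several provisions mean the data need not be balanced over periods:

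- SAP 9.1 randomises 18 subjects in blocks of six. Then: "The remaining two subjects will be randomly placed in 2 of the 6 treatment sequences". Sequence sizes are therefore 4, 4, 3, 3, 3, 3.
- SAP Section 5: "Only subjects with results from two or more periods will be included in comparisons". Two-period subjects stay in.
- SAP 6.1: a dosing problem "will result in PK data from that period for that subject being excluded from all treatment arm comparisons" and summaries, from the affected time point onward.
- SAP 7.3.3: AUC0-inf, half-life and Kel "for naloxone by treatment and subject will only be included if the subject has 3 or more concentration values" on the terminal part of the curve and the fit is adequate.

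In the other direction, Protocol 4.5.2 says of replacements: "A replacement subject will receive the same treatment as the subject being replaced".

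**The concern.** Period is a design factor in a crossover. If log exposure drifts from Day 1 to Day 7 and period is not modelled, the drift goes into the residual and the treatment interval widens. In a test for a difference that would be conservative. Here it is not, because the rule passes any interval that covers 1, so noise helps the conclusion.

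The Introduction of the protocol names a less than dose-proportional increase as the possibility of interest, and proportionality is a secondary endpoint. The stake is that a real shortfall becomes harder to detect. A second, smaller effect comes from imbalance: part of any drift can enter the treatment ratio by chance, in either direction.

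A drift is conceivable. Each subject receives 4 + 4 + 2 = 10 sprays over the three dosing days, and Protocol 4.1.1 lists nasal oedema, congestion and inflammation among observed reactions. The 72-hour spacing limits carryover of drug but does not exclude a period trend. No document shows that one exists.

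**Working it through.** **The plan's own figures.** The SAP gives no power or precision figure for 7.3.2. Its only such figures are in Table 4-1, for the concentration comparisons. All nine reproduce within 1 point with a one-sided paired t-test, n = 18, alpha 0.0221 and SD of the log difference √ln(1+CV²): 49.1, 90.7, 99.9 (A v C); 85.8, 94.2, 99.3 (B v C); 85.8, 87.9, 68.4 (B v A).

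**Assumptions.** The true dose-adjusted ratio is 0.80. CV is 48% (the Table 4-1 value at 15 min, as a stand-in), with 30% and 68% as the range. Within-subject correlation is 0.5, so the within-subject variance is σ² = ln(1+CV²)/2 and the log difference has variance 2σ² = ln(1+CV²), as in Table 4-1. The trend is a linear log step d per period. Steps of 0.05, 0.1 and 0.2 mean a Day 1 to Day 7 change of exp(2d) − 1 = 10.5%, 22% and 49%.

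**Balanced case, 18 completers.** The A v C estimate is the same with or without period. Omitting period changes the expected residual mean square from σ² on 32 df to σ² + 18·Σ(period deviation²)/34 = σ² + 36d²/34 on 34 df. The t quantiles are 1.694 and 1.691.

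At CV 48% and d = 0.2:

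- σ² = ln(1.2304)/2 = 0.1037, and 36 × 0.04/34 = 0.0424.
- Width ratio ≈ √(0.1461/0.1037) × 1.691/1.694 ≈ 1.185. The simulated mean is 1.179.
- SE with period = √(2 × 0.1037/18) = 0.1073, and |ln 0.80|/SE = 0.2231/0.1073 = 2.08. The noncentral t with 32 df then gives a 34.8% chance that the CI includes 1.
- Without period, simulation of the balanced case gives 46.7% (37.8% at d = 0.1).

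**Simulation with the SAP 9.1 allocation.** This used REML with a subject random intercept, with and without period, and two random dropouts (18 completers). Entries are the chance that the 90% CI for A v C includes 1, SAP model v model with period:

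| CV | d = 0.05 | d = 0.1 | d = 0.2 |
|---|---|---|---|
| 30% | 7.3 v 6.7% | 10.1 v 6.9% | 22.6 v 7.1% |
| 48% | 36.2 v 35.9% | 37.5 v 34.8% | 46.7 v 35.3% |
| 68% | 56.2 v 56.1% | 56.4 v 54.9% | 61.8 v 55.6% |

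Mean CI width ratios at CV 48% are 1.006, 1.044 and 1.179. At d = 0.03 the ratio is 0.998, so there is no widening. A further simulation at CV 48% and d = 0.2 gave coverage of the nominal 90% CI of 94.2% without period and 90.1% with it.

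Other completeness patterns at CV 48%:

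| Data | d = 0.05 | d = 0.1 | d = 0.2 |
|---|---|---|---|
| 20 completers | 32.0 v 31.3% | 33.5 v 30.9% | 42.0 v 30.7% |
| 2 of 20 miss period 3 | 33.5 v 33.7% | 34.8 v 32.2% | 44.7 v 33.1% |
| 15% of subject-periods missing | 41.2 v 41.6% | 43.7 v 41.2% | 50.9 v 40.0% |

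There were 15,000 trials per cell for 18 and 20 completers at CV 48% (Monte Carlo SE about 0.4 points), 10,000 at CV 30% and 68%, and 4,000 for the missing-period rows. Gaps below about 1 point carry no information.

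**Chance bias in the A/C log ratio without period.** The expectation is zero. The mean absolute size is 0.067d with 20 completers, 0.109d with two dropouts (worst case 0.389d) and 0.146d with 15% missing. At d = 0.1 that is about 0.7%, 1.1% (worst 4%) and 1.5% of the ratio.

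**The case against.** The strongest reply is that the harm needs a trend no document supports. Subjects are confined at one site from Day -1 to Day 8, meals are standardised, clinic staff give every dose, and doses are 72 hours apart. A 49% drift in six days is a strong assumption. At CV 48% a 10.5% drift moves the decision by less than 1 point, and with missing periods the SAP model then does no worse. This stands, and it limits the size of the concern.

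The imbalance argument is also modest. Its expected bias is zero, replacement on the same treatment tends to restore balance, the terminal-phase filter affects AUC0-inf but not Cmax or AUC0-t, and the dosing-problem exclusion runs only from the affected time point. This stands too.

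The decision rule is the larger defect. Even with period modelled, a 20% shortfall passes about 35% of the time at CV 48% and about 56% at CV 68%. Under an equivalence-type criterion, extra width would count against proportionality, so the direction of harm depends on this rule. That is correct, and adding period does not cure it.

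Finally, the endpoint is secondary, and the ratio with its CI is available alongside the pass/fail verdict. None of this shows that period is in the model or that leaving it out has any advantage beyond two degrees of freedom.

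**Conclusion.** The concern holds. The 7.3.2 model has no period term, and under the stated rule a material trend favours the conclusion of proportionality. For a true 20% shortfall with 18 completers, the omission raises the chance of that conclusion by less than 1 point at a step of 0.05, by about 1.5 to 3 points at 0.1, and by about 6 to 16 points at 0.2, over CVs of 68% down to 30%. The treatment ratio itself is essentially unbiased.

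These sizes rest on an assumed linear trend, assumed CVs and a within-subject correlation of 0.5, none of which the documents give for Cmax or AUC. The omission does not invalidate the analysis. It is worth correcting because the cost is close to nil, and because adding the term after the data of this open-label study are seen could look selective.

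**What to change.** In SAP 7.3.2, specify treatment and period (three levels) as fixed effects, with subject as a random effect on the intercept. No sequence term is needed, and no change to the paired t-test in 7.3.1 is proposed.

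The cost is one model term and two degrees of freedom. With no period effect, the 90% CI is about 0.6% wider with 18 completers (0.3% with 20), and the chance of including 1 at CV 48% moves from 34.6% to 34.9%. The includes-1 rule needs separate attention.

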
Safety Assessments:
	
Safety will be evaluated in terms of adverse events (AEs), clinical laboratory results (hematology, serum chemistry, and urinalysis), vital sign measurements (blood pressure, heart rate, respiratory rate, and oral body temperature), safety 12-lead ECG, and physical examination findings.
 
An examination of the nasal passage will be conducted by a trained observer to evaluate evidence of irritation to the nasal mucosa. This nasal irritation assessment will be taken at the following timepoints during study drug administration:
 
 • 0 (pre-dose), 4.5, 10, 30, 60, 240 minutes

Sample Size and Threshold Determination:
	
Approximately 20 healthy participants are planned for enrollment. The study is intended to obtain information regarding the pharmacokinetics and dose-proportionality of IN naloxone following different dosing schedules. The number of subjects was determined to have greater than 80% power for comparisons between treatment arms across prespecified consecutive timepoints (different timepoints for each comparison). These power calculations are based on 18 subjects with each comparison, allowing for potential dropouts. These analyses adjust for multiplicity using Pocock boundaries for assessing the same endpoint at multiple timepoints. Coefficient of variations and effects sizes for different treatment scenarios were determined using modeling and simulation from previous naloxone studies. Up to 4 subjects may be qualified as replacements, if needed.

Statistical Methods:
	
All data will be presented in data listings. Data from subjects excluded from the PK population will be presented in the data listings but not included in the calculation of summary statistics. The number of subjects who enroll in the study and the number and percentage of subjects who complete each assessment will be presented. The frequency and percentage of subjects who withdraw or discontinue from the study and the reason for withdrawal or discontinuation will be summarized. Demographic and baseline characteristics will be summarized overall and by treatment for all subjects.
 
Descriptive statistics will be used to summarize demographic and baseline subject characteristics. For continuous variables, the mean, median, standard deviation (SD), minimum, and maximum values will be reported.

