This involves a 2-3 minute delay between each dose and re-administering to a previously dosed nostril starting with the 3rd dose, which may result in a less than dose-proportional increase in naloxone plasma concentration and/or delayed increase in naloxone exposure compared to the first 2 doses. Obtaining data with repeat dosing will inform if and how fast naloxone plasma concentrations can be reached to be able to reverse highly-potent opioid overdoses.

This study will be a randomized, unblinded, three-way crossover study to determine naloxone plasma concentration after administration of multiple doses of IN naloxone:

- A. Four 4 mg IN naloxone doses (1 dose every 2.5 minutes)
- B. Four 4 mg IN naloxone doses (2 doses every 2.5 minutes)
- C. Two 4 mg IN naloxone doses (1 dose every 2.5 minutes)

IN naloxone (NARCAN Nasal Spray)

Intranasal naloxone is available as a 2 mg or 4 mg dose of naloxone hydrochloride in 0.1 mL with the indication to re-administer additional doses every 2 to 3 minutes (using alternating nostrils) if needed until emergency medical assistance arrives. The 4 mg drug is distributed in packages of two nasal sprays (1 dose per nasal spray), but additional doses can be administered if needed and available.

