3.2 Secondary Endpoints

1. First timepoint when there is a higher naloxone plasma concentration in the 4 naloxone dose arm B (2 doses every 2.5 minutes) compared to the 4 naloxone dose arm A (1 dose every 2.5 minutes)
2. Dose-proportionality of the 4 naloxone dose arms in reference to the 2 naloxone dose arm based on C_{max} , AUC_{0-inf} , and AUC_{0-t}
3. Predicted time to rescue a patient from simulated opioid-induced respiratory depression from fentanyl and carfentanil following medium and high overdose scenarios

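### SAP 7.3.2 concludes dose proportionality whenever the 90% CI includes 1, so imprecise data favour that conclusion and a real shortfall in exposure can be missed

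*SAP*

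**What the plan says.** Dose proportionality is the second secondary endpoint: "Dose-proportionality of the 4 naloxone dose arms in reference to the 2 naloxone dose arm" (Protocol 3.2), judged on Cmax, AUC0-inf and AUC0-t. In SAP 7.3.2 these parameters are "normalized to per mg of naloxone administered", log-transformed and analysed in a linear mixed model with treatment fixed; "Subject will be included as a random effect on the intercept". Then "Geometric mean ratio and 90% CIs will be obtained by exponentiation of the treatment effect", and the decision rule is: "Dose-proportionality will be concluded if the confidence interval includes 1".

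The SAP gives no equivalence limits, precision requirement or power for this conclusion. Protocol 4.9.5 has no criterion of its own and leaves PK analysis details to the SAP, and the Protocol's section on analysis populations says the SAP prevails where the two differ. The SAP rule is therefore the operative one.

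The topic is not incidental. The Protocol Introduction says that repeated dosing involves returning to an already dosed nostril, "which may result in a less than dose-proportional increase in naloxone plasma concentration". The Protocol synopsis, under sample size, says: "The study is intended to obtain information regarding the pharmacokinetics and dose-proportionality of IN naloxone following different dosing schedules".

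**The concern.** After normalisation per mg, exact proportionality is a geometric mean ratio of 1, and less than proportional exposure is a ratio below 1. The rule takes failure to reject a ratio of 1 as grounds to conclude that it equals 1. This has three consequences:

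- A wide interval counts in favour of proportionality. Losing subjects or seeing higher variability makes the conclusion more likely.
- A very precise estimate close to 1, of no practical importance, can be declared non-proportional.
- The burden of proof falls on the shortfall that the Protocol gives as a reason to study repeat dosing.

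At stake is the reported answer on a named secondary endpoint. Four sprays could be described as delivering dose-proportional exposure when they do not.

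**Working it through.** **1. Reproduce the plan's own figures.** The documents give no power for proportionality. The only design calculation is SAP Table 4-1 (power for early concentrations, n = 18, one-sided 0.0221, paired comparison of logs). With SD of the log difference = √ln(1+CV²), SE = SD/√n and the noncentral t with n−1 df, the results are:

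- A vs C: 49.1, 90.7, 99.9% (stated 49, 91, 100)
- B vs C: 85.8, 94.2, 99.3% (stated 86, 94, 99)
- B vs A: 85.8, 87.9, 68.4% (stated 86, 88, 68)

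All nine agree, so the SAP treats its CV as that of the within-subject log difference. The same convention is used below.

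**2. Inputs.** n = 18 (Protocol 4.9.1); 90% CI (SAP 7.3.2); df = 2(n−1) = 34, for three treatments with complete data. CVs of Cmax and AUC are **assumed** at 20–68%, because the documents give none; 48% and 68% are the Table 4-1 values for A vs C at 15 and 10 minutes.

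**3. Probability that the rule concludes proportionality.** For true ratio R, let δ = ln(R)/SE and let c be the 95th percentile of t on 34 df (1.691). Then

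P(CI includes 1) = F(c; 34, δ) − F(−c; 34, δ), where F is the noncentral t distribution function.

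Example, CV 48%, R = 0.80: SD = √ln(1.2304) = 0.455; SE = 0.455/√18 = 0.107; δ = −0.223/0.107 = −2.08; P = 35%.

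| CV | SE (n=18) | R=0.85, n=18 | R=0.80, n=18 | R=0.70, n=18 | R=0.80, n=12 |
|---|---|---|---|---|---|
| 20% | 0.047 | 4% | 0.1% | 0% | 2% |
| 30% | 0.069 | 26% | 6% | 0% | 18% |
| 48% | 0.107 | 56% | 35% | 5% | 50% |
| 68% | 0.145 | 71% | 56% | 22% | 66% |

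Using n−1 df instead raises these by at most about 2 percentage points. If the CV is instead a within-subject CV per treatment (SD × √2), the R = 0.80, n = 18 column becomes 28%, 58% and 72% at CV 30, 48 and 68%.

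**4. Effect of losing data.** At CV 48% and R = 0.80, the probability is 31% with 20 subjects, 35% with 18 and 50% with 12. Some loss is foreseeable: SAP 6.1 excludes data after dosing problems, and SAP 7.3.3 omits AUC0-inf without at least three terminal points and an adjusted R² above 0.80.

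**5. What one result could look like.** At CV 68% and n = 18 the interval is the estimate multiplied and divided by exp(1.691 × 0.145) = 1.28. An observed ratio of 0.79 gives 0.79/1.28 = 0.62 to 0.79 × 1.28 = 1.01, and the rule concludes proportionality.

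**6. The reverse error.** At CV 20%, n = 18 and R = 0.95, the CI includes 1 in 71% of trials, so 29% are declared non-proportional. At R = 1 the figure is 10% for any n.

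**7. An equivalence rule for comparison.** Limits of 0.80–1.25 are illustrative and not from the documents. If the whole 90% CI must lie inside them, then at R = 0.80 proportionality is concluded in about 5% of trials or fewer at every CV tried. At R = 1 and n = 18 (simulated) it is concluded in 87% (CV 30%), 31% (CV 48%) and 2% (CV 68%).

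**The case against.** The best defence is about consequence. Proportionality is a secondary endpoint; the sample size and primary endpoint rest on early concentrations and do not use this rule. The ratio and its 90% CI are obtained anyway, so a reader could see imprecision whatever label is attached. The PK/PD modelling uses the PK data, not the yes/no verdict. The Introduction raises under-proportionality as one possibility, alongside delayed exposure.

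The size is also uncertain. The 48–68% CVs come from single early time points and may overstate variability in AUC. At 20% a 20% shortfall is almost never missed. Under the SAP's SD convention, shortfalls of 40% or more are missed at most about 4% of the time with 18 subjects. Twelve evaluable subjects is a stress case, since the plan enrols 20 with up to 4 replacements. Finally, a 0.80–1.25 margin appears in neither document, and the study was not sized for it.

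All of this stands as a limit on the harm. None of it makes the rule valid: at any CV it draws a positive conclusion from a non-significant result. The margin objection bears on the choice of remedy, not on the fault.

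**Conclusion.** The concern holds. As written, the prespecified conclusion for a named secondary endpoint does not follow from the evidence the rule requires, and nothing else in either document corrects it.

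The practical size depends on the unknown Cmax and AUC variability. It is negligible for a 20% shortfall if the CV is near 20%, and about one in three to more than one in two if it is 48–68% with 18 subjects. The fault is greatest for modest shortfalls with noisy data.

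The same section also lists B versus A, where both arms receive 16 mg in total. Applied there, the rule would read non-significance as equal exposure between schedules.

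**What to change.** Replace the decision sentence in SAP 7.3.2 by one of the following, before concentration data are available:

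- **With a margin.** *Dose proportionality is concluded only if the 90% CI of the dose-normalised geometric mean ratio lies wholly within prespecified limits (for example 0.80–1.25). A departure is concluded if the CI excludes 1 and is not wholly within those limits. Otherwise the result is inconclusive.* The sponsor must justify the limits.
- **Without a margin.** Delete the yes/no conclusion and report each ratio with its 90% CI.

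In either case, describe B versus A as a comparison of exposure at equal dose.

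The cost is SAP wording only. With a margin, inconclusive results will be common if variability is high: 80% power at a true ratio of 1 needs about 17, 37 or 67 subjects at CV 30, 48 or 68% (n−1 df, limits 0.80–1.25). The estimation-only option needs neither a margin nor extra subjects, and suits a study sized for a different question.
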